### 2.2 Secondary Objectives and Endpoints

The secondary objectives of this study are:

- To assess the safety, tolerability, pharmacokinetics (PK), and pharmacodynamics (PD) of oral vadadustat once daily dosing in Japanese subjects with anemia secondary to NDD-CKD during the 6-week, primary efficacy period
- To evaluate the effect of dose adjustments and demonstrate the maintenance effect on Hb during a 10-week dose-adjustment and maintenance period
- To assess the time to reach the target Hb range from baseline

The efficacy endpoints that will be used to assess these objectives include the following:

- Time to reach target Hb level of 10.0-12.0 g/dL from baseline visit (Day 1)
- Mean Hb levels at the end of the primary efficacy period (Week 6) and at the end of the dose adjustment and maintenance period (Week 16)
- Proportion of subjects who achieve target Hb 10.0-12.0 g/dL at the end of the dose adjustment and maintenance period (Week 16)
- Mean change in Hb between pre-treatment and the end of the dose adjustment and maintenance period (Week 16)
- Mean change in hematocrit, red blood cell (RBC) count, and reticulocyte count from baseline to the end of the primary efficacy period (Week 6) and the end of the dose adjustment and maintenance period (Week 16)
- Mean change in iron indices (ie, iron, total iron-binding capacity [TIBC], transferrin saturation [TSAT], and ferritin) and hepcidin from baseline to the end of the primary efficacy period (Week 6) and the end of the dose adjustment and maintenance period (Week 16)
- Proportion of subjects requiring rescue with RBC transfusion from baseline to the end of the primary efficacy period (Week 6) and the end of the dose adjustment and maintenance period (Week 16)
- Proportion of subjects requiring rescue with ESAs from baseline to the end of the primary efficacy period (Week 6) and the end of the dose adjustment and maintenance period (Week 16)
- Number of dose adjustments from baseline to the end of the dose adjustment and maintenance period (Week 16)
- Maintenance of iron sufficiency (defined as ferritin  $\geq 50$  ng/mL and TSAT  $\geq 20\%$ ) from baseline to the end of the primary efficacy period (Week 6) and the end of the dose adjustment and maintenance period (Week 16)
- Plasma concentration profile of vadadustat and its metabolites using pre-dose sample from Week 4

The safety endpoints that will be used to assess these objectives include the following:

- Safety assessments, including adverse events (AEs), vital signs, electrocardiograms (ECGs), and other laboratory assay results (eg, chemistry, components of the complete blood count [CBC] other than the ones noted above, and vascular endothelial growth factor [VEGF])

### 3 INVESTIGATIONAL PLAN

[figure not shown]
#### 3.1 Overall Study Design and Plan

This is a Phase 2, randomized, double-blind, placebo-controlled, dose-finding study to assess the efficacy, safety, tolerability, PK, and PD of orally administered vadadustat in Japanese subjects with anemia secondary to NDD-CKD.

The study has a planned enrollment of 48 subjects to be enrolled at approximately 25 sites in Japan. There will be 16 subjects in each of the 3 tablet-count groups.

An overview of the study design is presented in Figure 1.

Figure 1: Overview of Study Design

\* For subjects who develop an excess Hb response during the primary efficacy period, the number of tablets of study drug will be decreased (see Section 8.2.4). For these subjects, the number of tablets of vadadustat initiated at the Week 6 visit will be lower than indicated.

The study will include the following periods:

- Eligibility screening period (up to 4 weeks)
- Primary efficacy period (6 weeks; Weeks 1 to 6)
- Dose adjustment and maintenance period (10 weeks; Weeks 7 to 16)
- Follow-up period (2 weeks; Weeks 17 and 18)

Subjects will participate in a screening period (4 days to 4 weeks) to determine study eligibility, and eligible subjects will be randomized following the screening period.

Using a central randomization system, subjects will be randomized 1:1:1 to receive 1, 2, or 4 tablets at their baseline visit (Day 1). Within each tablet-count group, subjects will be randomized 3:1 to receive vadadustat (150, 300, or 600 mg vadadustat) or placebo. See the protocol section 8.2.2 for information regarding the randomization scheme.

Study drug treatment will be administered during a 6-week primary efficacy period. See the protocol section 8.2.4 for information on study drug administration. The primary efficacy period includes fixed-dose treatment to establish a dose-response relationship. However, if Hb level increase rapidly or if the Hb level exceeds 13.0 g/dL, the study drug dose can be decreased or interrupted (see the protocol section 8.2.4).

After completing the primary efficacy period, subjects will continue to a 10-week dose adjustment and maintenance period (see the protocol section 8.2.5). Subjects receiving placebo will be switched to vadadustat, and study drug dose will be adjusted to achieve a target Hb of 10.0-12.0 g/dL based on dose adjustment guidelines (see the protocol section 8.2.5).

Vadadustat treatment will stop after the dose adjustment and maintenance period has been completed (Week 16) and subjects will continue in a 2-week follow-up period (Week 17-18).

The clinical and safety assessments will be performed as described in the protocol section 9.3 and as listed in the protocol Appendix A.

### **3.2 Efficacy and Safety Variables**

#### **3.2.1 Efficacy and PD Variables**

The following variable is the primary efficacy variable:

- Change from pre-treatment in Hb at Week 6.

The following efficacy endpoints will also be analyzed:

- Actual values and change (absolute and percent) from pre-treatment in Hb, hematocrit, RBC count, and reticulocyte count (both absolute and percent)
- Actual values and change (absolute and percent) from pre-treatment in iron, TIBC, TSAT, ferritin, and hepcidin

#### **3.2.2 Safety Variables**

The following variables are the safety endpoints:

- AEs
- Vital signs
- ECGs
- Laboratory parameters

#### **3.2.3 PK Variables**

The following variables are the PK variable:

- Pre-dose plasma concentrations of vadadustat at the Week 4 visit
- Pre-dose plasma concentrations of vadadustat's metabolites at the Week 4 visit

## **4 STATISTICAL METHODS**

### **4.1 Data Quality Assurance**

All tables, figures and data listings to be included in the report will be independently checked for consistency, integrity and in accordance with standard PAREXEL procedures.

### **4.2 General Presentation Considerations**

'Pre-treatment' of Hb is defined as the average of 2 Hb values obtained prior to treatment based on the qualifying screening Hb value and the Hb value at the Baseline Visit. 'Pre-

treatment' for other variables is defined as the last available pre-treatment assessment. In general, this is the value at the Baseline Visit. 'End of Treatment (EOT)' is defined as the assessment on the EOT form labeled as 'Week 16 Visit', even if other values closer to Day 113 are available. 'Treatment Day' will be calculated relative to start of dosing at Baseline Visit (i.e. Treatment Day = Assessment Date - Baseline Visit Date + 1).

Continuous data will be summarized in terms of the mean, standard deviation (SD), median, minimum, maximum and number of observations, unless otherwise stated. The minimum and maximum will be reported to the same number of decimal places as the raw data recorded in the database. The mean and median will be reported to one more decimal place than the raw data recorded in the database. The SD will be reported to two more decimal places than the raw data recorded in the database. In general, the maximum number of decimal places reported shall be four for any summary statistic.

Categorical data will be summarized in terms of the number of subjects providing data at the relevant time point (n), frequency counts and percentages. Any planned collapsing of categories will be detailed in the SAP text and the data displays.

Percentages will be presented to one decimal place. Percentages will not be presented for zero counts. Percentages will be calculated using n as the denominator. If sample sizes are small, the data displays will show the percentages, but any textual report will describe frequencies only.

Changes from baseline in categorical data will be summarized using shift tables where appropriate.

P-values greater than or equal to 0.001, in general, will be presented to three decimal places. P-values less than 0.001 will be presented as "<0.001".

Confidence intervals will be presented to one more decimal place than the raw data.

All report outputs will be produced using SAS® version 9.3 or a later version in a secure and validated environment. All report outputs will be provided to the Sponsor in a single Microsoft Word 2010 [Version 14.0] document.

## **4.3 Study Subjects**

### **4.3.1 Disposition of Subjects**

A clear accounting of the disposition of all subjects who enter the study will be provided, from screening to study completion.

The summary of the following subject disposition will be presented.

- A summary of the number of subjects randomized, the number and percentage of subjects treated (with at least one dose of study medication) and the number and percentage of subjects completed through Week 6 Visit and discontinued by Week 6 Visit by treatment group and overall (Analysis population: All Subjects

Randomized). For final analysis, a summary of the number and percentage of subjects completed Week 18 Visit and discontinued from the study by treatment group and overall will be provided (Analysis population: All Subjects Randomized). Withdrawals from the study will also be summarized by major reason.

By-subject listings of eligibility details, randomization details, visit dates and withdrawal/study completion details (including reason for discontinuation and duration of treatment prior to discontinuation) will be provided.

#### **4.3.2 Protocol Deviations**

Major protocol deviations are defined as those deviations from the protocol likely to have an impact on the perceived efficacy and/or safety of study treatments. The impact of major protocol deviations on the efficacy and/or safety results will be evaluated prior to unblinding to determine which data and/or subjects, if any, to exclude from the analysis populations (see Section 4.4),

Protocol deviations and any action to be taken regarding the exclusion of subjects or affected data from specific analyses will be determined in Protocol Deviation Specification document 20170207 version 2.0.

The protocol deviation will be summarized as following:

- A summary of the number and percentage of subjects with a protocol deviation by treatment group and overall and by type of deviation and by period (Analysis population: All Subjects Randomized)

A by-subject listing of protocol deviations will be provided.

#### **4.4 Analysis Populations**

Upon database release, protocol deviation and analysis population outputs will be produced and will be sent to Sponsor for review. An analysis population classification meeting will be arranged to discuss the outputs and to decide which subjects and/or subject data will be excluded from certain analyses. Decisions made regarding the exclusion of subjects and/or subject data from analyses will be made prior to unblinding and will be documented and approved by Sponsor.

The following summary of analysis population will be provided:

- A summary of the number and percentage of subjects allocated to each analysis population by treatment group and overall (Analysis population: All Subjects Randomized)

A by-subject listing of analysis population details will be provided. This listing will be presented by treatment group and include: site, subject identifier, inclusion/exclusion flag

for each population and reason for exclusion from each population. All subjects randomized will appear on this listing.

#### 4.4.1 Analysis Population for the Safety Analyses

The safety summaries and analyses will be based on the **safety population**. The safety population is defined as all enrolled subjects who receive at least 1 dose of study medication. In the event that a subject is allocated the incorrect study treatment as per the study randomization list, subjects will be summarized and analyzed 'as treated' i.e. by allocated treatment group.

#### 4.4.2 Analysis Populations for the Efficacy Analyses

The efficacy summaries and analyses will be based on the **modified intent-to-treat (MITT) population**. The MITT population is defined as all randomized subjects who have received at least 1 dose of study medication and have a pre-treatment Hb average defined as the average of the qualifying screening value and the baseline value, and at least one post-baseline Hb measurement. In the event that a subject is allocated the incorrect study treatment as per the study randomization list, subjects will be summarized and analyzed 'as randomized' i.e. by randomized treatment group.

For the efficacy variables, sensitivity analyses will be performed on the **per-protocol (PP) population** to assess the robustness of the study conclusions to the choice of analysis population. The PP population is defined as the subjects in the MITT population who have completed the study and have efficacy data through Week 6, have a study medication compliance of  $\geq 80\%$ , and do not have any major protocol deviations expected to significantly affect the primary efficacy endpoint. Subjects with major protocol deviations expected to significantly affect the primary efficacy endpoint will be identified and documented prior to data unblinding.

#### 4.4.3 Analysis Population for the PK Analysis

The PK summaries and analyses will be based on the **pharmacokinetics (PK) population**. The PK population is defined as all subjects in the safety population who have a pre-dose PK sample at Week 4. Subjects will be summarized and analyzed by actual treatment group.

#### 4.5 Demographic and Other Baseline Characteristics

The demographic and other baseline characteristics will be summarized for the MITT and safety populations. The following summaries will be provided:

- A summary of demographic variables (e.g. age, gender, weight, height and body mass index [BMI]) by treatment group and all subjects

- A summary of other relevant variables (e.g. estimated Glomerular Filtration Rate [eGFR] at baseline, CKD stage, etiology of CKD and smoking status) by treatment group and all subjects
- A summary of relevant medical history by treatment group and all subjects.
- A summary of prior and concomitant medications within 30 days prior to the first study drug dose up to and including Week 6 by treatment group and overall.
- For the final analysis, a summary of concomitant medications after Week 6 will be provided.

Age will be calculated as the number of complete years between a subject's birth date and the date of informed consent.

Definitions of eGFR and CKD stage are described in section 4.8.4.8.

CKD stage will be determined by eGFR at baseline:

CKD stage	eGFR (mL/min/1.73m  )
1	90+
2	60 - 89
3a	45 - 59
3b	30 - 44
4	15 - 29
5	< 15

By-subject listings of demographic data and other baseline characteristics (as summarized above) will be provided

## 4.6 Treatment Compliance

The treatment compliance will be summarized for the MITT and safety population. The following summary will be provided.

- A summary of the treatment compliance measures (i.e.  $\geq 80\%$  compliance and  $< 80\%$ ) by treatment group and study visit.

A by-subject listing of treatment compliance data will be provided.

## 4.7 Efficacy Evaluation

### 4.7.1 Analysis and Data Conventions

This study is designed to test for dose-response relationship. An analysis of covariance (ANCOVA) model will be used to compare absolute change from pre-treatment in Hb between the three vadadustat dosing groups and the placebo group. The model will include treatment assignment (3 dosed groups and one placebo group) and pre-treatment Hb value as a covariate. A step-down procedure will be used to control the overall type I error rate for the multiple comparisons. Testing of the highest dose compared with

placebo will be conducted first. If and only if this comparison is significant, then testing will proceed to comparison of the next lower dose and placebo, and so on. Therefore, no multiplicity adjustment will be needed for this analysis.

A linear regression dose-response modeling will be performed as a secondary analysis.

$$Y = \beta_0 + \beta_{dose}X$$

where Y is change in Hb and X is vadadustat dose.  $\beta_{xs}$  are parameters of the model.  $\beta_0$  is intercept and  $\beta_{dose}$  is slope, respectively.

The null hypothesis for the dose response will be that the regression coefficient of slope parameter is zero. The alternative hypothesis will be that the regression coefficient is not zero. Symbolically, this is expressed as follows:

$$H_0: \beta_{dose} = 0$$
$$H_1: \beta_{dose} \neq 0$$

This hypothesis will be tested using a 0.05 two-sided significance level.

#### 4.7.1.1 Multi-center Studies

Not Applicable. Analysis of center effect is not planned.

#### 4.7.1.2 Adjustments for Covariates

The primary efficacy analysis will be adjusted for the pre-treatment measure of primary efficacy variable.

An ‘unadjusted’ sensitivity analysis will be performed to assess the robustness of the study conclusion.

#### 4.7.1.3 Handling of Missing Data

For the MITT population analyses for the primary efficacy variable, the Last Observation Carried Forward (LOCF) approach will be used to impute missing data.

- If a Baseline value is missing, the last value prior to baseline will be carried forward to the Baseline value but not to further values during the treatment period.
- For post-Baseline assessments, hemoglobin measurements at end of treatment and follow-up visits are not carried forward. Other than that, the most recent post-baseline assessments to the primary evaluation period (week 6) will be carried forward. Baseline and pre-Baseline values will not be carried forward to the post-Baseline visits.

For the secondary endpoint analyses, data will be used as observed and no imputation method will be used.

#### 4.7.1.4 Multiple Comparisons/Multiplicity

Analysis of one primary variable [Change in Hb] and one time point of primary interest [Week 6 visit] has been defined for this study. Though 3 pairwise comparison between placebo and dosed group is planned, step-down procedure will be used to control the overall type I error rate. The secondary variables defined are intended to provide supportive evidence relating to the primary objective and no labeling claims are intended. Though one preliminary analysis is planned before the final analysis, primary analysis will not be changed. Hence no adjustments for multiplicity are required.

#### 4.7.1.5 Preliminary (6-Week) Analysis

After all subject performed assessment of the Week 6 Visit, preliminary analysis will be performed. As the study conduct and final analysis will not be modified by this analysis, no alpha adjustment is proposed. It is expected that this 6-week data will be identical for the preliminary analysis and the final analysis of the complete dataset. Any changes between the preliminary analysis and the final analysis will be documented. The preliminary analysis will be performed by the independent unblinded team. All data through the cutoff date of the last subject randomized who completes week 6 will be analyzed. Blinding of blinded team and investigators will be maintained to prevent potential bias.

#### 4.7.1.6 Examination of Subgroups

Not Applicable. No subgroup analysis is planned.

### **4.7.2 Primary Efficacy Variable – Mean Change in Hb from Pre-treatment to the End of the Primary Efficacy Period (Week 6)**

The primary variable for the assessment of efficacy is the change from pre-treatment to Week 6 in Hb (g/dL). Change in Hb is defined as the Hb measured at the Week 6 visit minus the mean pre-treatment Hb. Pre-treatment Hb is defined as the average of 2 Hb values obtained prior to treatment based on the qualifying screening Hb value and the Hb value at the baseline visit.

For the primary analysis, the LOCF approach will be used to impute missing data. Complete-case analysis will be performed for sensitivity at the scheduled Week 6 visit.

#### 4.7.2.1 Summary of actual value and change in Hb at week 6

The primary analysis population for efficacy will be MITT and PP population. The following summary will be provided:

- A summary of actual value of Hb by treatment group at baseline and week 6. A summary of the change (absolute and percent) from baseline in Hb by treatment group at week 6. 1st and 3rd quartiles (Q1, Q3) as well as the mean, SD, median, minimum, maximum and number of observations will be shown. P values for overall comparison and treated groups vs. placebo on change from baseline will also be presented.

- A waterfall plot for absolute Hb change from baseline for each treatment group at week 6.

The effect of treatment in terms of the change from pre-treatment to Week 6 in Hb will be analyzed using a one-way analysis of covariance (ANCOVA). The statistical model will assess the main effect of treatment, adjusted for pre-treatment average. Least-squares (LS) means for each treatment and their 95% confidence intervals (CIs) will be presented. Three post-hoc pairwise comparison, i.e., Placebo vs 150 mg, placebo vs 300 mg, and placebo vs 600 mg, will be done. Unadjusted one-way analysis of variance (ANOVA) will be performed for sensitivity.

The simple linear regression between the change from pre-treatment to Week 6 in Hb and dose will be calculated. The regression coefficients and their standard errors, p-values of test of regression parameters and their 95% CIs will be presented. The test of slope parameter will be used to evaluate dose response relationship.

As sensitivity analyses, efficacy endpoints will also be analyzed using the PP population.

A by-subject listing of actual values and change (absolute and percent) from baseline in Hb will be provided.

#### 4.7.2.2 Summary of actual value and change in Hb from baseline to week 6 and beyond

The analysis population for efficacy will be MITT and PP population. The following summary will be provided:

- A summary of actual value of Hb by treatment group and study visits. 1st and 3rd quartiles (Q1, Q3) as well as the mean, SD, median, minimum, maximum and number of observations will be shown. Summary of pre-treatment average will also be presented.
- A summary of the change (absolute and percent) from baseline in Hb by treatment group and study visits.
- A plot showing the mean Hb value over time within each treatment group. 95% CI of these means will be shown as error bar and sample size in each group at each time point will be shown.
- Plots of individual profile of Hb values over time within each treatment group.
- Box plots of absolute Hb changes from baseline for each treatment group at each post-treatment study visit to week 6
- Box plots of absolute Hb changes from baseline for each treatment group at each post-treatment study visit to week 16

A by-subject listing of actual values and change (absolute and percent) from baseline in Hb will be provided.

### 4.7.3 Secondary Efficacy Variables

The analysis population for efficacy will be MITT and PP population.

Time to reach target Hb Range

Time to reach target Hb level of 10.0-12.0 g/dL from baseline is defined for subjects with Hb <10.0 g/dL at the baseline visit as following:

First post-treatment assessment date with value of Hb  $\geq 10.0$  and  $\leq 12.0$  g/dL – the baseline visit date +1. If target Hb level is not achieved, last Hb assessment date will be used as censored date.

A summary of time to reach target Hb level will be provided for subjects with Hb <10.0 g/dL at the baseline visit by treatment group.

Kaplan-Meier failure (cumulative incidence) plot will be presented for the time to reach target Hb level by treatment group.

A by-subject listing will be provided.

Hb within target Range

A summary of the number and percentage of subjects within target Hb 10-12 g/dL at the end of the dose adjustment and maintenance period (Week 16) will be provided by treatment group.

The number and percentage of subjects above / within / below target range who are maintained within the target range at their previous visit after Week 6 will be provided by treatment group.

The effect of treatment in terms of the proportion of subjects within target Hb level at Week 6 will be analyzed using Fisher's exact test. Three post-hoc pairwise comparison, i.e., placebo vs 150 mg, placebo vs 300 mg, and placebo vs 600 mg, will be done.

A by-subject listing will be provided.

Increase in Hb from pre-treatment average

A summary of the number and percentage of subjects who achieved a  $\geq 1$  g/dL increase in Hb from pre-treatment average will be provided by treatment group.

The effect of treatment in terms of the proportion of subjects who achieved a  $\geq 1$  g/dL increase in Hb from pre-treatment average will be analyzed using Fisher's exact test. Three post-hoc pairwise comparison, i.e., Placebo vs 150 mg, placebo vs 300 mg, and placebo vs 600 mg, will be done.

Hematocrit, RBC count, and reticulocyte count

Hematocrit, RBC count, and reticulocyte count (both absolute and percent) will be analyzed as secondary efficacy variables.

The following summaries will be provided:

- A summary of hematocrit, RBC count, and reticulocyte count (both absolute and percent) by treatment group and time point. 1st and 3rd quartiles (Q1, Q3) as well as

the mean, SD, median, minimum, maximum and number of observations will be presented.

- A summary of the change (absolute and percent) from baseline in hematocrit, RBC count, and reticulocyte count (both absolute and percent) by treatment group and time point
- Box plots of absolute changes from baseline in hematocrit, RBC count, and reticulocyte count (both absolute and percent) for each treatment group at each post-treatment time point

The effect of treatment in terms of the change from baseline to Week 6 in hematocrit and RBC count and reticulocyte count (both absolute and percent) will be analyzed using ANCOVA. The statistical model will assess the main effect of treatment, adjusted for baseline measurement. LS-means for each treatment and their 95% CIs will be presented. Three post-hoc pairwise comparison, i.e., Placebo vs 150 mg, placebo vs 300 mg, and placebo vs 600 mg, will be done. Unadjusted ANOVA will be performed for sensitivity.

A by-subject listing of hematocrit, RBC count, and reticulocyte count (both absolute and percent) will be provided by treatment group.

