#### Maintenance of iron sufficiency

A summary of maintenance of iron sufficiency (defined as ferritin  $\geq 50$  ng/mL and TSAT  $\geq 20\%$ ) from baseline to the end of the primary efficacy period (Week 6) and the end of the dose adjustment and maintenance period (Week 16) will be provided.

The effect of treatment in terms of the proportion of subjects who maintain iron sufficiency will be analyzed using Fisher's exact test for week 6 only. Three post-hoc pairwise comparison, i.e., Placebo vs 150 mg, placebo vs 300 mg, and placebo vs 600 mg, will be done.

A by-subject listing of iron sufficiency will be provided by treatment group.

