## 2 STUDY OBJECTIVES

### 2.1 Primary Objective and Endpoint

The primary objective of this study is to assess the dose-response relationship between oral vadadustat once daily dosing for 6 weeks and the change in Hb in Japanese subjects with anemia secondary to NDD-CKD; this is to define the starting dose for use in Phase 3 clinical studies in Japan.

The primary endpoint that will be used to assess this objective is the mean change in Hb levels from pre-treatment to the end of the primary efficacy period (Week 6). Pre-treatment Hb is defined as the average of 2 Hb values obtained prior to treatment based on the qualifying screening Hb value and the Hb value at the baseline visit.

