#### 4.7.1.4 Multiple Comparisons/Multiplicity

Analysis of one primary variable [Change in Hb] and one time point of primary interest [Week 6 visit] has been defined for this study. Though 3 pairwise comparison between placebo and dosed group is planned, step-down procedure will be used to control the overall type I error rate. The secondary variables defined are intended to provide supportive evidence relating to the primary objective and no labeling claims are intended. Though one preliminary analysis is planned before the final analysis, primary analysis will not be changed. Hence no adjustments for multiplicity are required.

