#### Increase in Hb from pre-treatment average

A summary of the number and percentage of subjects who achieved a  $\geq 1$  g/dL increase in Hb from pre-treatment average will be provided by treatment group.

The effect of treatment in terms of the proportion of subjects who achieved a  $\geq 1$  g/dL increase in Hb from pre-treatment average will be analyzed using Fisher's exact test. Three post-hoc pairwise comparison, i.e., Placebo vs 150 mg, placebo vs 300 mg, and placebo vs 600 mg, will be done.

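### The responder (rise of at least 1 g/dL) and iron-sufficiency proportions are tested without using dose order, which costs some power for the dose-response objective they are meant to support (minor)

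*SAP*

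**What the plan says.** The document holds three versions of the SAP. The references here are to the current text (Amendment 3), which tests the responder and iron-sufficiency endpoints in the same way as the preceding version.

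- Section 2.1 sets the aim: "The primary objective of this study is to assess the dose-response relationship between oral vadadustat once daily dosing for 6 weeks".
- Section 4.7.1.4 gives the role of the other endpoints: "The secondary variables defined are intended to provide supportive evidence relating to the primary objective and no labeling claims are intended".
- Section 4.7.3, on a rise of at least 1 g/dL: "increase in Hb from pre-treatment average will be analyzed using Fisher's exact test. Three post-hoc pairwise comparison". The three comparisons are placebo against 150, 300 and 600 mg.
- Section 4.7.3, on iron sufficiency, applies the test to the proportion of subjects "who maintain iron sufficiency will be analyzed using Fisher's exact test for week 6 only", followed by the same three comparisons.
- Section 4.7.3, on transfusion and ESA administration, plans the same set of tests.

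Dose order enters the testing only for the continuous change in haemoglobin: the step-down from the highest dose in Section 4.7.1, and the linear regression on dose in Sections 4.7.1 and 4.7.2.1.

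**The concern.** The plan provides an ordered test for the continuous primary variable but none for the binary variables said to support it. An overall Fisher test gives the same p-value however the four dose labels are permuted. Each pairwise test uses only half of the subjects. If the proportion climbs with dose, a test aimed at that ordering has more power from the same data.

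At stake is how the supportive results read in a study meant to define a Phase 3 starting dose. With a real gradient, the planned tests may report that only 600 mg differs from placebo, or that nothing differs, more often than they need to.

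**Working it through.** **Inputs from the SAP (Section 4.10).** 12 subjects in each of 4 groups; mean Week 6 change 0 g/dL on placebo and 1.35 g/dL on 600 mg; common SD 0.68 g/dL; two-sided alpha 0.05 for the primary comparison; stated power above 95%.

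**Assumptions.** The SAP gives no means for 150 and 300 mg, no rescue or iron-sufficiency rates, and no significance level for the Fisher tests. I take means linear in dose unless stated, two-sided 0.05, no missing data, and Week 6 as the responder time point, which the responder paragraph does not name.

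**Step 1: the plan's own figure.** Noncentrality = 1.35 / (0.68 × √(2/12)) = 1.35 / 0.2776 = 4.86. With 22 df, power is 99.6%, which agrees with the stated figure.

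**Step 2: the slope test on haemoglobin change.** Mean dose is 262.5 mg. Sxx = 12 × (262.5² + 112.5² + 37.5² + 337.5²) = 12 × 196,875 = 2,362,500, with square root 1,537. Slope = 1.35/600 = 0.00225. Noncentrality = 0.00225 × 1,537 / 0.68 = 5.09. With 46 df, power is 99.9%.

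**Step 3: responder rates.** P(change ≥ 1) = 1 − Φ((1 − μ)/0.68):

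- μ = 0: 1 − Φ(1.471) = 7%
- μ = 0.3375: 1 − Φ(0.974) = 17%
- μ = 0.675: 1 − Φ(0.478) = 32%
- μ = 1.35: 1 − Φ(−0.515) = 70%

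**Step 4: exact power.** All 13⁴ outcomes were enumerated. Given the total number of responders S, a table (x₁…x₄) has null probability ∏C(12, xⱼ)/C(48, S). The overall Fisher p-value sums the tables no more probable than the one observed. The exact Cochran-Armitage p-value sums the tables at least as extreme in |Σ(dⱼ − d̄)xⱼ|, with d = 0, 150, 300, 600 mg. Power is the sum of ∏Binomial(xⱼ; 12, πⱼ) over tables with p ≤ 0.05. The four planned tests are the overall Fisher test and the three pairwise tests.

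| Pattern (0/150/300/600 mg) | Overall Fisher | Any of the four planned tests | Exact trend |
|---|---|---|---|
| Responder, plan's effect, linear: 7/17/32/70% | 87% | 91% | 96% |
| Responder, concave means 0/0.6/1.0/1.35: 7/28/50/70% | 86% | 92% | 93% |
| Responder, 600 mg effect 1.0, linear: 7/14/23/50% | 55% | 61% | 76% |
| Responder, 600 mg effect 0.8, linear: 7/12/19/38% | 33% | 38% | 54% |
| Iron, assumed 90/82.5/75/60% | 25% | 32% | 43% |
| Iron, assumed 90/80/70/50% | 42% | 51% | 62% |
| Iron, assumed 90/80/65/45% | 53% | 62% | 72% |
| Rescue, assumed 30/20/10/2% | 30% | 35% | 47% |
| Rescue, assumed 10/6/3/0% | 3% | 3% | 8% |
| Plateau, assumed 7/50/50/50% | 66% | 79% | 40% |
| Non-monotone, assumed 20/50/65/45% | 45% | 59% | 15% |

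At the plan's effect, the pairwise tests have 1.5%, 16% and 88% power for 150, 300 and 600 mg. Two or more doses differ from placebo in only 16% of trials. The trend test is significant when none of the four planned tests is in 5.5% of trials at the plan's effect, and in 16.5% at an effect of 1.0 g/dL.

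**Step 5: false positives.** With a common rate of 7%, 30% or 50% in all groups, the exact trend test rejects in 2.4%, 4.0% and 4.0% of trials. At least one of the four planned Fisher tests rejects in 1.3%, 6.1% and 7.6%.

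**The case against.** **Dose-response is already tested.** The slope test uses dose order and all subjects, with about 99.9% power under a linear effect. The responder endpoint is a dichotomy of the same haemoglobin change, and the proportions are tabulated by dose group, so a gradient would be visible. This stands. A reader might infer that the trial neglects dose-response, or that these endpoints cannot support it. The SAP does not bear that out.

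**The supportive role is stated only in general terms.** Section 4.7.1.4 is one sentence on multiplicity and disclaims labelling claims. Section 2.2 lists iron sufficiency and rescue under the secondary objectives and does not list the responder endpoint. This lowers the priority, but Section 4.7.1.4 still makes no exception for these endpoints.

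**Power is already good at the plan's effect.** A reader might infer that a graded effect would often be missed. On the plan's figures that is not so: the overall Fisher test misses 13% and the four planned tests together 9%, against 4% for the trend test. The larger losses need a smaller effect than planned, or iron and rescue rates the SAP does not give. With rare rescue (10/6/3/0%) every test fails, and the cause is 12 per arm.

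**A trend test can do worse.** Under the plateau it loses 26 points to the overall Fisher test (40% against 66%). Flattening at the top is plausible, because Section 3.1 allows dose reduction before Week 6 and Section 4.7.1.3 analyses those subjects as observed. This argues against replacing the Fisher test, not against adding to it: under the plateau, trend plus pairwise tests detect an effect in 80% of trials, against 79% for Fisher plus pairwise.

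**A significant trend does not prove a gradient.** Under a 600-mg-only pattern (7/7/7/70%) the trend test has 98% power. This stands and limits the interpretation.

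**Conclusion.** The point holds as a minor inefficiency. The planned Fisher tests are valid, but they leave dose order unused for two endpoints described as supporting a dose-response objective. Against the overall Fisher test, the loss for monotone effects is 9 points at the plan's own effect with linear means (96 − 87) and 7 with a concave curve (93 − 86). It is about 20 points at smaller effects (76 − 55; 54 − 33) and at the assumed iron-sufficiency rates (18 to 20). Against all four planned tests together, the gain at the plan's effect is 5 points (96 − 91).

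These sizes rest on full groups of 12, two-sided 0.05, Week 6 assessment and a response monotone in dose. The iron figures also rest on rates the SAP does not state. The primary dose-response conclusion is unaffected.

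**What to change.** In Section 4.7.3, for the proportion with a rise of at least 1 g/dL at Week 6 and for iron sufficiency at Week 6, add an exact Cochran-Armitage trend test over the randomised groups with scores 0, 150, 300 and 600 mg, labelled supportive. Name Week 6 explicitly for the responder test. Keep the overall and pairwise Fisher tests as planned.

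Do not apply the trend test to the proportion within 10–12 g/dL, which need not be monotone in dose because of overshoot. Do not apply it after Week 6, when placebo subjects switch to vadadustat and doses are adjusted. Treat it as optional for transfusion and ESA use, where low event rates would leave any test with little power. State that a significant trend is to be read with the group proportions and does not by itself separate a graded response from an effect at 600 mg alone.

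The cost is a sentence or two of SAP text and one standard procedure call per endpoint, with no new data. It adds one more unadjusted supportive p-value per endpoint, and the trend test is weak for plateau or non-monotone patterns, which the retained Fisher tests cover.
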